1. INTRODUCTION

1.1 Basic Information

The optic nerve is made up of approximately one million nerve fibres that originate from retinal ganglion cells (RGC).

The nerve fibres of the optic nerve can be the site of degeneration processes due to different etiopathogenic mechanisms such as an increase of intraocular pressure (in the case of Glaucoma), ischemic phenomena (in arteritic and non-arteritic ischemic optic neuropathy) infective-inflammatory processes (in Optical Retrobulbar Neuropathy in the case of Multiple Sclerosis).

In particular, non-arteritic Ischemic Optic Neuropathy (NAION) (i.e., not related to autoimmune diseases) is a disease that can have an acute onset with a chronic progression and can affect one eye (monocular) or both (binocular). The disease causes a severe impairment of the visual function understood as decreased visual acuity (VA), loss or reduction of contrast perception, visual field deficits of various kinds in relation to the selective involvement of the optic nerve fibres: arcuate scotoma, blind-central scotomas, upper or lower altitudinal deficit.

From a pathogenetic point of view NAION is most frequently caused by transient hypoperfusion of the head in the optic nerve at level of the posterior ciliary arteries that causes a compartmental syndrome inducing ischemia. In rare cases it can be traced to local embolic phenomena (Hayreh 2011, Kerr et al. 2009).

The neurodegeneration process of the nerve fibres of the optic nerve can be assessed both from a functional point of view using Pattern Electroretinogram recording (PERG) and Visual Evoked Potential (VEP) (Parisi et al. 2008a) and the morphological view by studying the thickness of nerve fibers using optical coherence tomography (OCT) (Kernstock et al. 2014, Akbari et al., 2016, Han et al. 2016).

The literature reports the possibility, in rare cases, of slight spontaneous improvement of the visual function (Hayreh and Zahoruk 1981). However, there is currently no evidence of substantial benefit from specific therapies.

Indeed, currently under debate are the use of intravitreal injections of triamcinolone and anti angiogenics, oral steroid therapy, and intravitreal injection of erythropoietin (Kernstock et al. 2014).

In the case of another neurodegenerative disease of the optic nerve, Glaucoma, a concept recently proposed is for "neuroenhancement", i.e., the possibility of increasing the impaired function of the RGC and optic nerve (Chang and Goldberg 2012). This concept is based on data

relating to the increase of the responses of the PERG (an objective method of function of RGC) and VEP evaluation (an objective method of assessing the functionality of the optic nerve) after treatment with Cicitoline (Parisi et al. 1999). The increase in RGC functionality can produce, over time, protection mechanisms from the acceleration of the peculiar apoptotic processes of the glaucomatous disease with a consequent reduction in the number of RGC that undergo cell death (neuroprotection).

Citicoline is a natural precursor of phosphatidylcholine, which constitutes the main component of neuronal and mitochondrial membranes. Regarding the physiology of RGC, phosphatidylcholine performs two very important roles: one is structural, as it represents the main phospholipid membrane, and one is functional in that, following the action of the phospholipase A2 enzyme, it is a source of fatty acids (AA and DAG), fundamental intracellular messengers (Secades and Lorenzo 2006).

Currently Citicoline is available in oral solution, the bioavailability of which is well known, about 98% (Agut et al., 1983, Roda et al. 1983). In this regard, the evidence bearing particular importance for Citicoline, administered as an oral solution at a dose of 500 mg/day in 4-month treatment cycles followed by 2 months of suspension, is its ability to slow the progression of visual field loss in glaucoma patients where there is a documented progressive loss of the visual field in the two years prior to starting treatment with Citicoline (Ottobelli et al. 2013)

A pilot study, conducted on patients suffering from NAION, demonstrated that after months of treatment with Citicoline administered in oral suspension, there was improvement in ganglion cell functionality, nerve conduction along the visual pathways and visual acuity (Parisi et al. 2008b).

1.2 Effects of Citicoline on the function of ganglion cells and the optic nerve in patients with non-arteritic ischemic optic neuropathy

Our pilot study enrolled patients suffering with NAION in accordance with a set of inclusion/exclusion criteria which are listed comprehensively in the published work (Parisi et al. 2008b).

Patients with NAION were divided randomly into two groups matched by age:

- 1) NAION -T Group: 14 patients were treated with Citicoline. Citicoline was administered orally (Cebrolux - Tubilux, Italy, 1600 mg/day) for 60 days. followed by a suspension period of 4 months for a total of 6 months follow-up
- 2) NAION -NT Group: 12 patients were not treated and the natural evolution of the disease was observed during a follow-up of 6 months.

For this study, randomized for the first six months, it was decided in the sixth month of observation to continue the study as "open" and to continue to treat patients with NAION for a further period of 2 months, followed by 4 months of suspension.

For a more detailed description of the procedures followed and the electrophysiological techniques used, please refer to the original works. (Parisi et al. 2008a, Parisi et al. 2008b)

In analysing the VEP and PERG results, we considered the following parameters: P100 latency time and amplitude N75-P100 (VEP); latency time P50 and amplitude P50-N95 (PERG); difference between latency P100 and P50 (retinal cortical time, SCT).

During the study period the following was observed:

1. VEP: a decrease in the P100 latency time and an increase in amplitude N75-P100 after the two months of treatment; after the suspension period, we found a worsening in electrofunctional responses. At the end of the first follow-up (6 months) the VEP values were significantly different ($P<0.01$) both compared to those of the baseline and compared to those of the control group (NAION -NT).
2. PERG: a decrease in the P50 latency time and an increase in amplitude P50-N95 after the two months of treatment; after the suspension period, we found a worsening in these electrofunctional responses. At the end of the first follow-up (6 months) the PERG values were significantly different ($P<0.01$) both compared to those of the baseline and compared the control group (NAION -NT).
3. SCT: (electrofunctional index of post-retinal nerve conduction derived from the difference between the P100 latency time of the VEP and the P50 latency time of the PERG): a decrease after two months of treatment; after the suspension period we found a worsening of this electrofunctional index. At the end of the follow-up (6 months) the SCT values were significantly different ($P<0.01$) both compared to the baseline and compared the control group (NAION -NT).
4. VA: increase after two months of treatment; after the suspension period, we found a worsening of these psychophysical responses. At the end of the follow-up (6 months) the VA values were significantly different ($P<0.01$) both compared to the baseline and compared the control group (NAION -NT).

1.3 Citicoline mechanism of action

From the data available in the literature, it is known that the exogenous administration of citicoline causes an increase in endogenous phosphatidylcholine synthesis and thus accelerates the repair of the previously damaged cell membranes (Secades 2001).

The cell membrane dysfunction or degeneration induces the release of cytotoxic substances (lytic enzymes, excitotoxic amino acids, etc.) which induce an extension of the area of damage or activate the mechanisms that lead to apoptosis (for example, an increase in the concentration of intracellular ceramide, a compound produced by catabolism of sphingolipids, is a potent pro-apoptotic agent)

In particular, in the etiology of vascular diseases (for example in stroke) a loss of phospholipid components is found resulting from an alteration in their metabolism, which leads to irreversible damage to the cell membranes of neurons. Biochemically a loss of phosphatidylcholine is observed, which is degraded during the ischemic processes into fatty acids with the production of reactive oxygen species (ROS). Experimental studies suggest that the administration of citicoline induces a reactivation of the anabolism of the phospholipids with reduced degradation of phosphatidylcholine and thus reduced formation of ROS. In some animal models a reduction was also observed of the infarcted area volume after treatment with Citicoline.

Therefore the therapeutic approach with citicoline allows the maintaining and/or restoring of the integrity of the cell membranes of neurons subjected to ischemic insults, such as can occur in some of the many forms of glaucomatous syndrome.

1.4 Neuro-functional considerations on treatment with Citicoline systemically and safety and tolerability in humans

The fundamental element for cell function and survival is the ability to maintain an internal environment different to the external one. This function is ensured by the cell membrane, a discriminating barrier that selects and regulates the passage of the substances inside the cell and controls the difference in electrical potential.

Also, most of the biochemical reactions occur close to the cell membrane and in its context surface receptors are located allowing a dialogue of the cell with the surrounding cells and the rest of the organism.

In fact, the cell membrane:

- is the site of receptors and synapses that govern communications with neighbouring cells and the rest of the organism,

- maintains and controls the difference in electrical potential, which is necessary to allow propagation of the nerve impulse,
- handles most enzymatic reactions,
- at the mitochondrial level, the inner membrane is the site of the main energy production processes.

A lesion of the cell membrane leads to three important events:

1. some ions normally concentrated in the extracellular environment, in particular Ca^{++} , and other potentially harmful molecules, can enter uncontrollably into the cytoplasm, altering the vital processes of the cell
2. the ability to communicate through surface receptors is lost;
3. the intracytoplasmic content, rich in lytic enzymes and toxic mediators, can flow outside of the cell resulting in an extension of the damage to the contiguous cells. Therefore, an alteration of the phospholipids turnover compromises the validity of the membrane protection systems. Furthermore, as a result of activating the particular lytic enzymes, the phospholipases, the catabolism of the membrane phospholipids is accelerated and, if the resynthesis mechanism is insufficient, toxic molecules accumulate, such as ceramide, which can activate the metabolic pathways that lead to programmed cell death (apoptosis). To maintain the perfect functionality of the cells, therefore, the cell membrane needs to stay structurally intact. This is absolutely necessary in the case of cells without replicative capacity like the RGC, the loss of which results in irreversible functional impairment.

The cell membrane is composed of a double layer of phospholipids. Phospholipids are continuously exposed to chemical and physical insults which damage the molecular structure: to protect itself from this, the cell possesses an enzyme system that catabolises the damaged phospholipids and reuses the constituent elements (phosphocholine, glycerol and fatty acids), in order to synthesise them again

An alteration of the phospholipids turnover compromises the validity of the membrane protection systems and puts the specific cell functionality at risk. In the case of peripheral neurons such as RGC, the peculiar length of their axonal endings makes these cells particularly sensitive to any alteration in the cell membrane protection systems. In fact, precisely by virtue of the enormous development of the membrane surfaces, due to the length of their axons, these cells are more susceptible than others to the harmful effects caused by a phospholipid synthesis slowdown.

The clinical conditions where a slowdown of the phospholipid metabolism occurs are those

that present when the neural tissue undergoes a type of traumatic, ischemic or degenerative process.

In glaucoma and in NAION a pathological situation is configurated in which one or more of these 3 elements can contribute to the development of damage to the optic nerve. Both glaucoma and NAION are neurotropicopathies where alterations of the retinal structures are observed (Quigley et al. 1995, Parisi et al. 2008a) and retinal structures (Yucel et al. 2000).

An improvement of the VA, the VEP and contrast sensitivity after treatment with Citicoline was also observed in partially sighted patients (Porciatti et al., 1998, Campos et al., 1995, Campos 1997). These studies suggested that the effects observed were attributable to the activity of dopamine-like effect of Citicoline (Gottlob et al. 1989, Gottlob and Stangler-Zuschrott 1990). This pharmacological property could explain, at least partly, the positive effects of PERG and PEV observed in patients with glaucoma (Parisi et al. 1999, Parisi 2005 Rejdak et al. 2003) and in patients with NAION (Parisi et al. 2008b). In fact, it is known that levodopa induces a shortening of the VEP latency in humans with a possible retinal contribution as the PERG also is improved by this substance (Secades 2001). The VEP variations found in patients with glaucoma and with NAION are attributable to a dysfunction of the innermost retinal layers (ganglion cells and their fibres), correlated to a delay in post-retina nerve conduction (Parisi 2001, Parisi et al. 2001, Parisi 1997, Parisi et al. 2008a), while the PERG alterations can be attributed to a dysfunction of the innermost retinal layers, although the possibility of a functional alteration of the pre-ganglionic elements has also been suggested (Veagan et al. 1995, Parisi et al 2008a).

The improvements of the PERG can also be attributed to a dopaminergic-like action of Citicoline; in fact it has been observed that levodopa induces an increase in retinal function (Gottlob et al. 1989) and therefore a similar neuromodulating activity can be assumed to explain the effects of Citicoline.

In addition to the evaluation of retinal function, both in glaucoma patients and in those with NAION, postretinal nerve conduction was examined using SCT measurement (Celesia and Kaufmann, 1985). The reduction of the SCT, observed after treatment with Citicoline (Parisi et al. 2008b), can be attributed to an improvement of retinal function with consequent improvement of nerve conduction along the optic pathways and a related increase in bioelectric activity in those cells where cortical potential originates. And this may also explain the reduced latency and increased P100 amplitudes of the VEP after treatment with Citicoline.

Also the independent action of Citicoline on the postretinal nerve conduction or visual

cortex can be hypothesised, but this hypothesis has no clear, conclusive and appropriate experimental references in the literature.

Citicoline induces an improvement in retinal bioelectric activity: we are unable to demonstrate whether there are additional effects on retinal nerve fibres (for example an increase in the layer thickness of the retinal nerve fibre), since at this time only the retinal function has been studied and there have been no morphological assessments.

Therefore, the effects of Citicoline on the bioelectric responses of the visual cortex may derive from two sources of improvement: one at a retinal level (as indicated by the PERG with reduced latencies and increased amplitudes) and one at a postretinal level (as indicated by the shortening of the SCT). As has been recently observed, the perimetric indices (Mean Deviation of Humphrey perimetry) are significantly correlated with the parameters of PERG, VEP and SCT (Parisi 2001), thus it is likely that the sources previously mentioned as cortical improvement might also be suggested to explain the improvement in perimetric condition detected in patients with glaucoma after treatment with Citicoline (Pecori Giraldi et al. 1989).

In conclusion, our data suggest that Citicoline has a significant action in improving the retinal and cortical bioelectric responses in patients suffering from diseases of the optic nerve of glaucomatous or ischemic nature.

As a further benefit of this therapy, it should be emphasised that no clinical trial in humans (Parisi et al. 1999 Porciatti et al., 1998, Campos et al., 1995, Campos 1997 Virno et al. 2000 Rejdak et al., 2003) has reported significant adverse reactions either ocular or systemic.

1.5 Rationale of the study

The pilot study (Parisi et al 2008b) demonstrated the possibility of improving retinal functionality and nerve conduction along the optic pathways in patients suffering from NAION after treatment with Citicoline for oral suspension.

However, the limit of this study consisted in the fact that another dose of Citicoline (1600 mg/day) was used since the bioavailability (i.e. the presence of a percentage of active ingredient in the blood after a single administration) of this molecule administered in the formulation for oral suspension is certainly lower than that of intramuscular administration.

Currently Citicoline is however available in oral solution, the bioavailability of which is well known, about 98% (Agut et al., 1983, Roda et al. 1983), comparable to that of intramuscular administration. In this regard, the evidence bearing particular importance for Citicoline,

administered as an oral solution at a dose of 500 mg/day in 4-month treatment cycles followed by 2 months of suspension, is its ability to slow the progression of visual field loss in glaucoma patients where there is a documented progressive loss of the visual field in the two years prior to starting treatment with Citicoline (Ottobelli et al. 2013).

It will be particularly interesting to evaluate the changes in the function (via recordings of PERG) and morphology (via the OCT evaluations) of retinal and nerve conduction along the optic pathway (using VEP recordings) in patients with NAION who are treated with Citicoline oral solution whose bioavailability is well known.

2. OBJECTIVES AND AIMS OF THE STUDY

2.1 Primary objective

Evaluation of potential neuroprotective action of Citicoline for maintenance and stabilisation of visual acuity in patients with Non-arteritic Ischemic Optic Neuropathy (NAION).

2.2 Secondary objectives

- 1) to study the neurodegenerative processes of the optic nerve in patients suffering from NAION using the correlations between the function of RGC and optic nerve (using the PERG and VEP recording) and the structural modifications of the nerve fibres of the optic nerve (using the OCT evaluation);
- 2) to determine in patients with NAION the potential for neuroenhancement linked to Citicoline administration in oral solution. This will be obtained using the evaluations of the functional condition (PERG/VEP) found after treatment with Citicoline compared to the condition at the time of enrolment. Correlations will also be evaluated between stabilisation and/or function improvement of RGC and the optic nerve with changes in the visual field.
- 3) to study in patients with NAION the potential for neuroprotection linked to Citicoline administration oral solution. This will be evaluated by comparing, at the end of a 9-month follow-up period, the changes of the nerve fibre structure and the optic nerve (via the OCT assessment) found in the group of patients with NAION treated with Citicoline oral solution compared to a group of patients with untreated NAION where the natural progression of neurodegenerative processes will be observed.

4. STUDY POPULATION

A number of patients (from a minimum of 16 patients to a maximum of 32) will be enrolled, within a maximum time frame of 24 months, who have a diagnosis of unilateral or bilateral NAION aged 45 to 80 years such as to provide the study 32 eyes affected by this condition with the following

4.1 Inclusion criteria.

- 1) Acute visual reduction episode from NAION occurring for more than 6 months
- 2) Typical defects of the visual field evidenced with the Goldmann perimetry or with Humphrey perimetry 30-2
- 3) Visual acuity not less than 1/10
- 4) Having suspended any potential neuroprotective therapies (e.g., Coenzyme Q10) for at least 6 months.

4.2 Exclusion criteria

- Ocular surgery in the 3 months preceding the study, including surgery for cataracts in the previous three months.
- Cataract or maculopathy
- Known hypersensitivity to the study product
- Positive history for diseases of the optic nerve (retrobulbar optic neuropathy, glaucoma) or systemic diseases which could preclude the enrolment in the study according to the investigators' judgement
- Pregnant or nursing women, or women of potential childbearing age not using adequate contraception.
- Diabetes, SLE, rheumatoid arthritis, mixed connective tissue disease

5. TRIAL DESIGN

5.1 Trial Plan

A prospective, single-center, randomized, blinded close-label study providing for the enrolment of a minimum of 16 to a maximum of 32 patients (see sample size in the section "Statistics") affected by NAION.

Considering that according to the inclusion/exclusion criteria it is very difficult to recruit patients suffering from NAION with the specific characteristics that enable them to be enrolled in this study, it is likely that with the presence of the binocular NAION, both eyes of the patients will be considered as recruited. Therefore, in the event of all patients having monocular NAION, enrolment must include 32 patients and this number is lower if we need to enrol patients with NAION in both eyes.

Patients selected according to the inclusion/exclusion criteria after signing informed consent will be randomized into two groups:

- a) In one group of patients with NAION no type of treatment will be performed (16 eyes, Control Group)
- b) in another group of patients with NAION, Citicoline will be administered in oral solution (500 mg/day) for 6 months followed by three months of suspension (16 eyes, Treated Group)

The division into two groups will enable the identification of a specific neuroprotective action of Citicoline. Randomization will be done by dividing patients with similar characteristics including age, refraction and visual impairment (perimeter defect and visual acuity) into two groups. Patients will be assigned to each group by an investigator not involved in the functional and structural tests.

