6. ASSIGNMENT AND MASKING

Patients will be selected from a large cohort of known NAION patients who have been attending our facility for at least 12 months (approximately 125 patients). Only patients who meet the inclusion criteria will be selected. Patients will perform a baseline screening visit during which the conditions corresponding to the inclusion criteria will be evaluated and the study proposed. Only after signing the informed consent, will a single investigator ("recruiting doctor"), not involved in the clinical and instrumental assessments, decide whether to assign the selected patient to the Citicoline-treated or non-Citicoline-treated group.

The assignment to either group will take place in sequential order of presentation of the patient (with a 1:1 probability of being assigned to one or the other group) in order to constitute two homogeneous groups in terms of number.

The aforementioned assignment will be known only to the patient and the "recruiting doctor" who will not be involved in the clinical and instrumental assessments envisaged by the research and will therefore be the only investigating doctor to know the group to which the selected patient belongs; this feature of the study will be used to ensure "objectivity" of the clinical and instrumental assessments and to prevent them from being influenced in any way by the knowledge that the patient examined has or has not been treated with Citicoline. In this regard, it should be noted that the patient, by signing the informed consent, promises not to provide any type of information regarding the group to which he/she belongs and/or any treatment administered to other staff of the Institute involved in the clinical and instrumental assessments apart from the "recruiting doctor".

As a result, throughout the duration of the study (both at baseline and at the 6 and 9 month visits),

all study assessments (AV, CV, VEP, PERG, OCT) will be conducted by investigators who do not know if the patient being examined belongs to the Citicoline-treated or non-Citicoline-treated group.

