Based on known preliminary data (Parisi et al, 2008), considering the implicit time P100 of the VEP and a power value = 90% ($\alpha = 5\%$) it is deemed reasonable to include in the study $N = 11$ observations (eyes tested) per group. The sample number has been calculated based on the difference in the implicit time P100 of the VEP measured after 60 days of treatment with Cisticoline for oral suspension compared to the baseline of 15 ms (Baseline P100: mean 141 ms, a standard deviation; P100 at 60 days: mean 126 ms, a standard deviation: 9.8 ms).

To summarise, the size from the sample estimated on the basis of the primary objective (visual acuity) is $N= 5$; the size from the sample estimated on the basis of secondary objectives (PERG and VEP) is $N=12$ and $N=11$, respectively.

Considering the larger sample size ($N=12$, PERG), and assuming the presence of outliers and the potential voluntary withdrawal from the study by patients, the sample is increased by 30%, so it is considered appropriate to reach $N=16$ observations (eyes tested) per group (NAION Treated with Cisticoline and NAION not treated).

In this calculation of the sample, it is not possible to estimate a priori the sample number relative to the secondary objective – point 3 (see Point 2.2), as data in the literature are not currently available regarding possible changes in the structure of nerve fibres and the optic nerve (assessed by OCT) following treatment with Cisticoline.

The calculation procedure was carried out using the Minitab v.12.7 and Gpower 3.1 programmes, assuming that the averages and standard deviations of all the parameters considered come from two independent samples: Patients with NAION in baseline condition and patients with NAION after 60 days of treatment with Cisticoline in oral suspension (Parisi et al, 2008).

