9.2 General methodology

Data from repetitions of visual acuity tests, PERG, VEP, OCT will be expressed as the average difference between two recordings obtained during separate sessions + / - the standard deviation of this difference. The 95% confidence limits of the test-retest variability will be established by assuming a normal distribution of the data, after verification using the Anderson-Darling and Kolmogorov-Smirnov tests, calculating the average of the differences and the relative standard deviations.

For each group (NAION Control eyes and NAION eyes Treated with Cisticoline), differences in visual acuity values, PERG and VEP and OCT responses measured at 6 and 9 months from

baseline will be assessed using ANOVA and the $p < 0.05$ value will be considered significant. Multiple comparisons will be made using the Tukey and Games-Howell methods, establishing the value of the error rates at 5%.

Correlations between the electric-physiological measurements (PERG/VEP) and field of view measurements, normalized in logarithmic value, both at Baseline and at each follow-up time, for each group will be performed using Pearson's test and the $p < 0.05$ value will be considered significant.

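### Citicoline is assigned per patient, but sections 9.1 and 9.2 count eyes and make no allowance for two correlated eyes from one patient, so eye-level p-values are not reliably at 5%

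*Combined protocol and SAP*

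**What the plan says.** **Assignment is by patient.** Section 5.1 randomises patients to an oral solution or to no treatment. In section 6 a recruiting doctor is to "decide whether to assign the selected patient to the Citicoline-treated or non-Citicoline-treated group". Both eyes of a bilateral patient are therefore always in the same arm.

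**Enrolment is by eye.** Section 4 asks for 32 affected eyes: "A number of patients (from a minimum of 16 patients to a maximum of 32) will be enrolled". Section 5.1 expects bilateral patients to contribute two eyes ("it is likely that with the presence of the binocular NAION, both eyes of the patients will be considered as recruited") and adjusts the patient count from 32: "this number is lower if we need to enrol patients with NAION in both eyes".

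**Sample size is by eye.** Section 9.1 concludes: "it is considered appropriate to reach $N=16$ observations (eyes tested) per group (NAION Treated with Cisticoline and NAION not treated". The calculation was made "assuming that the averages and standard deviations of all the parameters considered come from two independent samples", the two samples being patients at baseline and patients after 60 days of treatment.

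**Analysis is by eye.** Section 9.2 reads: "For each group (NAION Control eyes and NAION eyes Treated with Cisticoline), differences in visual acuity values, PERG and VEP and OCT responses" at 6 and 9 months are assessed against baseline by ANOVA at p < 0.05, with Tukey and Games-Howell comparisons. It names no between-group test, although section 5.1 says: "The division into two groups will enable the identification of a specific neuroprotective action of Citicoline". Section 10.1 also expects treated patients to be compared with untreated ones.

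No section gives a patient effect, a patient average, a one-eye rule, a design effect or a between-eye correlation.

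**The concern.** Two eyes of one person share age, vascular risk, compliance and treatment arm, so they usually carry less information than eyes from two people. A test that treats them as separate observations then understates the standard error. Here this is a foreseen situation: section 5.1 calls recruitment very difficult and relies on second eyes to reach 32.

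At stake is whether a p-value below 0.05 means what it says, and whether the intervals have their stated coverage, for visual acuity (the primary objective) and for every secondary outcome. A smaller matter is that the 90% PERG power, which fixes the size of the trial, comes from a formula that holds only if the eyes are independent, and section 9.1 does not say so.

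**Working it through.** **1. Reproduce section 9.1.** Method: two independent means, two-sided 5% (assumed, since sidedness is not stated), 90% power, SD = sqrt((s1² + s2²)/2), noncentral t.

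- PERG: d = 0.38 / sqrt((0.29² + 0.25²)/2) = 0.38 / 0.271 = 1.404. This needs 11.72 eyes, so 12 per group, as stated (power 0.907).
- Inflation: 12 × 1.3 = 15.6, so 16, as stated.
- Visual acuity: d = 0.35 / sqrt((0.122² + 0.107²)/2) = 3.050. This needs 3.56, so 4; the plan states 5. The difference has no bearing here.

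The plan's final figure is therefore sound if eyes are independent.

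**2. What paired eyes do to the variance.** Let f be the share of an arm's eyes that come from bilateral patients, and rho the fellow-eye correlation (of changes, when change is tested). The variance of the arm mean is multiplied by 1 + f × rho. At rho 0.5, 16 eyes are worth:

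- 2 bilateral + 12 unilateral patients (f = 4/16 = 0.25): 16/1.125 = 14.2 eyes
- 4 + 8 (f = 0.5): 16/1.25 = 12.8 eyes
- 8 + 0 (f = 1): 16/1.5 = 10.7 eyes

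**3. Type I error of eye-level tests.** Simulation with no true effect, 16 eyes per arm, the same mix in both arms, 100,000 trials per cell. Rho and the mix are assumptions. Eye-level two-group t-test, nominal 5%:

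| Bilateral + unilateral patients per arm | rho 0.1 | 0.3 | 0.5 | 0.7 | 0.9 |
|---|---|---|---|---|---|
| 0 + 16 | 5.0% | 5.0% | 5.0% | 5.0% | 5.0% |
| 2 + 12 | 5.2% | 5.9% | 6.5% | 7.1% | 7.6% |
| 4 + 8 | 5.6% | 6.8% | 8.1% | 9.4% | 10.9% |
| 8 + 0 | 6.2% | 8.8% | 11.4% | 14.0% | 17.1% |

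The eye-level paired-change test within one group gives 5.2-7.7%, 5.5-10.8% and about 6-17% for the three bilateral mixes. Separate runs moved single cells by up to about half a point, so the ranges quoted elsewhere are slightly wider than the table. A repeated-measures ANOVA over the three visits gives about 7-11% at 4 + 8 and 10-18% at 8 + 0, for rho 0.3 to 0.7.

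**4. The other reading of section 9.2.** A one-way ANOVA that treats the three visits as independent leaves between-eye variation in its error term and is conservative for that reason. Clustering pushes the other way. Over rho 0.1 to 0.9:

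- visit correlation 0.5: about 0.5-2.7% at 4 + 8, and 0.8-6.8% at 8 + 0
- visit correlation 0.7: never above 2.0% in any mix
- visit correlation 0.3: up to 12.9% at 8 + 0

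**5. PERG power at 16 eyes per arm, analysed on patient means.**

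- All independent: 0.970.
- Half the eyes from bilateral patients (4 + 8): 0.946 / 0.936 / 0.931 / 0.921 / 0.911 at rho 0.1 / 0.3 / 0.5 / 0.7 / 0.9.
- All bilateral (8 patients): the SD is multiplied by sqrt((1 + rho)/2). At rho 0.5 the effect is 1.404/0.866 = 1.62 and power is 0.854. Over the same rho values, power is 0.940 / 0.899 / 0.854 / 0.808 / 0.764.

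Visual acuity power stays at or above 0.998 on the same formula.

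**6. Check of the remedy.**

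- Welch t-test on patient means: 4.7-5.1% in all mixes and at all rho, including unequal bilateral shares between arms.
- ANCOVA on patient means: 4.8-5.2%.
- Random-patient model for eye changes: 3.5-5.3%.

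**The case against.** The strongest reply is that the inflated rates belong to tests section 9.2 does not name. It specifies ANOVA within each group, no between-group test, and multiple-comparison methods usually meant for independent groups. If visits are treated as independent, the error is mostly below 5% (step 4). Section 10.1 also speaks of comparing patients, so a patient-level comparison is not excluded. This stands, and it means the direction of the error cannot be read from the plan. It does not rescue the plan: a rate that may be 1% or 11% depending on an unstated choice is not controlled at 5%.

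Three stronger readings are tempting, and the documents do not support them.

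- *That the trial will have a false-positive rate near 17%.* That needs every patient to be bilateral and a correlation of changes of 0.9. Sixteen patients is the floor of a range, not an expected mix, and changes may correlate less than levels do. With 2 bilateral patients per arm and rho 0.1 to 0.3, the error is only 5.2-5.9%.
- *That section 9.1 asserts independent fellow eyes.* Its independence statement concerns baseline against 60 days. On fellow eyes it is silent; the assumption enters through the formula.
- *That the trial is too small.* Keeping 90% PERG power and the 30% allowance would take 12 × (1 + 0.5 × 0.3) × 1.3 = 17.9, so 18 eyes per group, up to 12 × 1.7 × 1.3 = 26.5, so 27 (rho 0.3 to 0.7, half to all eyes from bilateral patients). But PERG is a secondary objective, its power at 16 retained eyes is still above 0.90 when half the eyes are paired, and the primary outcome has ample power.

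**Conclusion.** The concern holds in conditional form. Assignment is by patient, inference is by eye, the plan expects second eyes, and nothing handles their correlation. If bilateral patients enter and rho is positive, eye-level two-group, paired-change and repeated-measures tests run above 5%. For the two-group and paired-change tests the error is about 5.2-7.8% at 2 + 12, 5.5-10.9% at 4 + 8 and 6-17% at the extreme of 8 + 0. If all patients are monocular there is no excess. If the ANOVA treats visits as independent, the error is mostly too low instead. On either reading, with bilateral patients in the trial, the eye-level p-value cannot be relied on to be at 5%.

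The sizes rest on assumed values of rho and of the bilateral share, on equal variances, and on normal data. That the unit of analysis is left unaddressed rests on the text alone. It should be settled before the assignment key is opened, so that the choice is not made with results in view.

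**What to change.** **Section 9.2.** Make the patient the unit of inference.

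- For each outcome, average the change from baseline over a patient's study eyes. Compare the two groups on these patient values with a Welch t-test, or with ANCOVA on the patient-mean baseline. Welch is preferred to the pooled test because bilateral patients may fall unevenly between arms.
- Use the same patient means for a paired test of change within each group.
- A mixed model is an acceptable alternative if it has a patient-level term for change. Patient and eye intercepts alone cancel out of a change and would not correct the error.
- For the correlations of PERG and VEP with the visual field, compute Pearson's r on patient means. A patient-cluster bootstrap interval is not advised: with 8 to 16 patients per group it wrongly excluded zero in about 8-11% of simulated trials, against 4-7% for Pearson on patient means.

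**Section 9.1.** State that the 90% power assumes independent eyes, give the size in patients as well as eyes, and report power over a range of rho (including values below 0.3) and bilateral share. No increase in enrolment is asked for.

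**Cost.** Wording only, submitted as an amendment under section 15.1. No added patients, visits or tests. Intervals will be wider and the stated PERG power less favourable. If fellow eyes prove independent, a little efficiency is lost: PERG power about 0.95 instead of 0.97 at 4 + 8.
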